Other attempts to reduce CAUTI include the development of different types of catheters. Standard indwelling catheters are made from a variety of materials including polyvinyl chlorine, plastic, plain latex, polytetrafluoroethylene, silicone elastomer, pure silicone hydrogel and polymer hydromer⁸. More recently, specialized catheters have been developed which involve coating the inner, outer or both surfaces of the catheter with antimicrobial materials⁹. These materials can be antibiotic or antiseptic with the most common antiseptic material used being silver. Silver ions are bactericidal, are used safely when applied topically to humans and used in controlling infections¹⁰.

Previous studies of latex-based catheters have demonstrated that use of silver alloy impregnated catheters reduced the incidence of CAUTI.¹¹ The magnitude of this reduction has been reported to range from 27% to 73%¹²⁻¹⁵ in prospective randomized trials. These numbers are strengthened by a recent meta-analysis which concluded that silver alloy catheters significantly reduced bacteriuria by 3-fold compared with standard catheters¹⁶. Although the previous work demonstrates encouraging results in decreasing CAUTI, the studies have varied in patient population, clinical indication and definition of outcomes. Moreover, there are no previous studies evaluating the effectiveness of silver alloy impregnated catheters for suprapubic use.

Urogynecology patients undergoing pelvic reconstructive surgery require bladder drainage in the immediate post-operative period. This can be achieved by placement of either a transurethral or suprapubic catheter (SPC). Although the SPC is more invasive compared to a transurethral catheter, the SPC is used routinely in many gynecologic surgical practices because of its' many advantages. These include prevention of urethral trauma and stricture formation, decreased UTI¹⁷,¹⁸, increased patient satisfaction compared to chronic indwelling urethral catheters, less discomfort¹⁹, avoidance of urethritis²⁰, maintained ability to void spontaneously, easier nursing care²¹, and shorter hospital stay¹⁸. Review of literature does not demonstrate any benefit with any particular type of SPC²².

We hypothesize that this study will show a statistically significant decrease in UTI rate among the urogynecology patients undergoing suprapubic catheterization with a silver-alloy catheter compared to the standard catheter.

Schematic Design of the Study: randomized control trial

Aims:

- 1) To compare the UTI rate among women undergoing urogynecological procedures with a silver-alloy suprapubic catheter compared to the standard supra-pubic catheter.
- 2) To identify risk factors predisposing patients to suprapubic CAUTI.

Methods

Description of Recruitment Methods:

How will subjects be identified?

Individuals who are being scheduled for a surgery which routinely requires placement of suprapubic catheter intraoperatively (i.e. abdominal sacrocolpopexy, anterior vaginal colporrhaphy, Burch colposuspension with and without mid-urethral sling), will be approached about participating in the study in the pre-operative urogynecology clinic.

How will subjects be contacted?

Subjects will be contacted in the Urogynecology clinic during the pre-operative visit. They will also be contacted during their routine 6-week follow-up post-operative visit in Urogynecology clinic. Additionally, if a patient has symptoms of a UTI or seeks medical treatment for a UTI during the 6 week post-operative period, we will ask the patient to contact the study team.

Recruitment Materials (if applicable):

n/a

Subject Population:

Number (total, each subgroup) 444 total, 222 per group

Gender:

Male	0
Female	444

Ages: 18 to 99 years

Inclusion Criteria:

- patients requiring intra-operative placement of suprapubic catheters as part of routine post-operative care for repair of anterior compartment prolapse i.e. patients undergoing anterior colporrhaphy, Burch colposuspension, with or without mid-urethral sling

Exclusion Criteria:

- Known UTI at time of surgery

- Unable to provide informed consent
- Use of chronic intermittent self-catheterization pre-operatively
- Use of chronic prophylactic antibiotics
- Use of antibiotics for any indication other than UTI during peri-operative and 6-week post-operative period
- Presence of fistula involving urogenital tract
- Use of chronic steroids or immunosuppressant
- Immunocompromised patient

Step-by-Step Schedule (include all procedures, therapies – attach a table or flow chart if there are multiple procedures or visits and indicate the window of number of days in which the participant may return for follow-up visits):

1. Informed consent obtained pre-operatively to participate in study
2. Collection of baseline information including demographics, stage of prolapse, past medical history, past surgical history, history of past UTI, laboratory studies including collection of urine for urinalysis and bacterial gram stain and culture.
3. Computer-generated randomization of subjects to either the control group (standard non-latex foley catheter) or the treatment group (silver alloy-impregnated catheter), in blocks of 4.
4. Patients and study staff involved in outcome assessment will be blinded to type of treatment allocation.
4. Removal of catheter per standard post-operative catheter care (adequate urinary output over 24 hours, lack of gross hematuria, able to void voluntarily)
5. If a patient has symptoms of a UTI or seeks medical treatment for a UTI during the 6 week post-operative period, we will ask the patient to contact the study team.
6. Review of patient and medical records at 6 week follow-up visit for UTI and laboratory evidence, if available.
7. If suprapubic catheter still in place, sending urine sample obtained by catheter for urinalysis, bacterial gram stain and culture.

Biospecimen (types, number, volume, processing, storage): n/a

Plan for Dose Modification if Toxicity occurs (if applicable): n/a

Statistical Considerations

Endpoints

Primary: UTI rate

UTI is defined as:

- (1) any symptoms (fever $> 38^{\circ}\text{C}$, suprapubic tenderness, costovertebral angle tenderness, or otherwise unexplained systemic symptoms such as altered mental status, hypotension, or evidence of a systemic inflammatory response syndrome) requiring antibiotic treatment
- (2) urine culture with $> 10^5$ cfu / mL
- (3) urine culture with $> 10^3$ cfu/ mL and evidence of pyuria (dipstick positive for leukocyte esterase and/or nitrite, microscopic pyuria, or presence of microbes seen on Gram stain of unspun urine)²²

Secondary:

Power Statement:

Previous studies of transurethral latex catheters have demonstrated a reduction in CAUTI incidence of ranging from 27% to 73%¹²⁻¹⁵ with use of silver-impregnated catheters compared to standard latex foley catheters. Additionally, a previously published data from our center reported a CAUTI rate of 19%²³ with use of standard foley catheters used for SPC in a postoperative urogynecology population. Therefore, since there are no previous studies evaluating the CAUTI rate of silver-impregnated SPC use, a conservative estimate of 10% reduction will be used in our sample size calculation.

To obtain 80% power, with a difference in UTI rate of 10%, then the sample size per group that we hope to recruit is 400. However, we anticipate 10% drop-out so we will plan to recruit 222 per group, summing 444 total participants.

Data Analysis:

Continuous variables will be compared using a two sided t-test with alpha ≤ 0.05 considered statistically significant. Binary outcomes (UTI vs. no UTI) will be compared using Fisher's exact test. Descriptive statistics will be used to describe continuous variables for the two types of catheters. Multiple logistic regression will be used to adjust for confounders such as prior UTI, duration of catheterization, type of surgery performed, age, BMI, and comorbid conditions. Strength of association between UTI rate and confounders will be assessed by calculating odds ratios and their corresponding 95% confidence intervals.

Human Safety Aspects

Risks: The literature review does not reveal any added adverse effects of using silver-alloy catheters, above standard non-silver-alloy coated catheters. Since all patients, regardless of study participation, will have SPCs placed post-operatively as part of routine care, we do not anticipate any additional risks to participants.

Individual Subject Stopping Rules (if applicable): n/a

DSMB (if applicable):

Members:

n/a

Charter:

n/a

Stopping Rules for Efficacy and Safety (if applicable):

n/a

Questionnaires that ask about Depression (if applicable)

Included in study? Yes No

If "Yes", state the plan of management for subjects with possible depression:

References

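### The exclusion for non-UTI antibiotics reaches into the 6 weeks after surgery, so randomised women can meet it, and no analysis population says whether they stay in the primary comparison

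*Combined protocol and SAP*

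**What the plan says.** The criterion stands under Subject Population, Exclusion Criteria: "Use of antibiotics for any indication other than UTI during peri-operative and 6-week post-operative period". Long-term prophylaxis has its own line in the same list, "Use of chronic prophylactic antibiotics", so what this line adds is mainly use around and after surgery.

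The Step-by-Step Schedule gives the order of events. Step 1 is "Informed consent obtained pre-operatively to participate in study". Step 3 is "Computer-generated randomization of subjects to either the control group" or the silver-alloy group. The inclusion criterion has the catheter placed during the operation, so allocation must be settled by then. The next step adds: "Patients and study staff involved in outcome assessment will be blinded to type of treatment allocation". At 6 weeks the records are reviewed for UTI and laboratory evidence; no step records antibiotics given for other reasons.

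The Power Statement says: "However, we anticipate 10% drop-out so we will plan to recruit 222 per group". Data Analysis says: "Binary outcomes (UTI vs. no UTI) will be compared using" Fisher's exact test. Neither section defines an analysis population or gives a rule for a woman who meets an exclusion after randomisation.

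**The concern.** An eligibility criterion should be decidable before allocation. Actual antibiotic use in the 6 weeks after surgery is not. Enforcing this criterion would drop randomised women because of a later event, and that event is related to infection in a trial whose endpoint is infection. The comparison would then rest on women selected after allocation, not on the randomised groups.

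The plan does not say whether such women are withdrawn, left out of the analysis or kept, nor whether the drop-out allowance covers them. The denominator of the primary test is therefore not fixed in advance. A choice made once UTI results are known would be hard to defend.

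**Working it through.** **Timing.** Consent is step 1 and randomisation step 3, the allocated catheter is placed in the operation, and the 6-week period follows. The post-operative part of the criterion therefore falls wholly after randomisation. Part of the peri-operative element might be known earlier; the documents do not define it.

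**The plan's own figure.** The inputs are a control rate of 19% (Power Statement), a difference of 10% read as absolute (19% v 9%), and 10% drop-out. 222 × 0.9 = 199.8, or about 200 evaluable per group. The exact two-sided 5% Fisher test then has 79.4% power, close to the stated 80%. (The two-sided 5% level is stated for the t-test and assumed here for Fisher's test. The printed 400 per group fits only as a total: 400/0.9 = 444.4.) The 222 therefore leaves no separate room for exclusions after randomisation.

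**Bias with no true effect.** Let p be the true UTI rate, and let fe and fn be the shares of events and non-events removed. The observed rate is

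p(1 − fe) / [p(1 − fe) + (1 − p)(1 − fn)].

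Take p = 19% in both arms and 200 per group. All removal shares are assumed, because the documents give no antibiotic rate. Differences are control minus silver. False-positive rates are from 40,000 simulated trials per case.

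| Removed, silver v control | Observed silver | Observed control | Difference (points) | False positives |
|---|---|---|---|---|
| Events only, 20% v 10% | 0.152/0.962 = 15.80% | 0.171/0.981 = 17.43% | 1.63 | about 6% |
| Events only, 10% v 20% | 17.43% | 15.80% | −1.63 | about 6% |
| Events 20% v 10%, non-events 10% v 5% | 0.152/0.881 = 17.25% | 0.171/0.9405 = 18.18% | 0.93 | 4.8% |
| Events 10% v 5%, non-events 20% v 10% | 0.171/0.819 = 20.88% | 0.1805/0.9095 = 19.85% | −1.03 | 4.7% |
| Events and non-events alike, 20% v 10% | 19% | 19% | 0.0 | 4.2% |

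The fifth row shows that unequal removal alone causes no bias. With no true effect, removal must depend on UTI status, and differently in the two arms.

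**Reference rate.** Fisher's exact size at exactly 200 v 200 is 3.66%, but that is a low point caused by discreteness; at 199 v 201 it is 4.3%. The fair comparator is about 4.2-4.3%, the rate when removal is unrelated to UTI.

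**Power at 19% v 9%, if the loss comes on top of drop-out.**

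- 10% lost: 200 × 0.9 = 180 per group. Power is 74.2% at exactly 180 v 180, and about 77% when the numbers removed vary at random.
- 20% lost: 200 × 0.8 = 160 per group. Power is 68.9% at exactly 160 v 160, and about 71-72% when the numbers vary.

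The equal-size figures are again low points: one extra woman in the control group at 181 v 180 gives 75.0%.

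**The case against.** The strongest reply is that removal is inferred. The line sits among the eligibility criteria, no text tells the team to withdraw a randomised woman or leave her out, and the individual stopping rules are marked not applicable. The line might have meant use expected at screening. This stands in part: a reader might infer that the plan orders exclusion from the analysis, and the documents do not say so. But the line is not limited to expected use, unplanned use would still need a rule, and enforcing the line as an exclusion does drop randomised women.

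The second reply is blinding. Patients and outcome staff are blinded, which limits one route to arm-dependent removal. This also stands in part. The documents do not say who would apply the criterion or whether treating clinicians are blinded, and blinding sets no numerical bound.

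Third, the effects are modest. Only the events-only cases exceed 5% false positives, and there is no further power loss if these women fall within the 10% drop-out. Both points are correct.

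A reader might also infer that the endpoint and the exclusion collide, because definition (1) of UTI ends in "evidence of a systemic inflammatory response syndrome) requiring antibiotic treatment" and a woman with fever treated for another infection could meet both. That holds only if the three definitions are alternatives and the antibiotics in (1) need not be for UTI. The text settles neither, so the point here does not rest on it.

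**Conclusion.** The concern holds as a faulty eligibility rule combined with a missing analysis population. That part rests on the documents' own sequence of steps and needs no assumption.

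The consequence is less certain. A reader might infer that the primary result will be biased, or biased towards silver. The documents do not support that: bias arises only if women are removed and removal is tied to UTI status differently by arm, and the direction can go either way. In the assumed cases with no true effect the shift is at most about 1.6 points, with about 6% false positives against 4.2-4.3%; mixed removal shifts the difference by about 1 point and stays below 5%. These are illustrations, not bounds. The power cost is likewise conditional: about 74-77% or 69-72% instead of about 79% if 10% or 20% of women are lost beyond drop-out, and nothing further if they fall within it. It should be fixed before outcomes are examined.

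**What to change.** 1. Limit the eligibility exclusion to non-UTI antibiotic use known before randomisation. The sponsor should reconcile what the peri-operative part covers.
2. State in Data Analysis that the primary Fisher comparison includes every randomised woman with outcome data, in her assigned group, whatever antibiotics she later receives.
3. Record later non-UTI antibiotics, with date and indication.
4. Run a supportive sensitivity analysis leaving those women out.

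The cost is one eligibility line, one or two analysis sentences and a short data entry.

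The downside is dilution if later antibiotics prevent UTIs in both arms. Assume that 10% of women take them, at the same underlying risk as the rest, with 200 per group:

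- Half of their UTIs prevented: 19% × 0.95 = 18.05% v 9% × 0.95 = 8.55%, a difference of 9.5 points and power of about 77%.
- All prevented: 17.1% v 8.1%, a difference of 9.0 points and power of about 74%.

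If 20% take them, the differences are 9.0 (17.1% v 8.1%) or 8.0 points (15.2% v 7.2%), with power of about 74% or 67%. Leaving the same women out gives about 74-77% (10%) or 69-72% (20%). In these assumed cases, keeping them costs little or no power relative to removing them, and it preserves the randomised comparison.

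### Randomising in a single stated block size of 4, with the operating team not listed as blinded, could make up to one third of allocations certain in advance; randomly varying blocks would remove most of that cheaply

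*Combined protocol and SAP*

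**What the plan says.** Step 3 of the Step-by-Step Schedule describes computer-generated allocation to the control group "or the treatment group (silver alloy-impregnated catheter), in blocks of 4". This is the only statement about how the sequence is built. No strata, varying block size, list holder, central release or sealed envelopes are described.

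The first of the two items numbered 4 in the same schedule sets the blinding: "Patients and study staff involved in outcome assessment will be blinded to type of treatment allocation". The operating team is not on that list. The inclusion criteria cover "patients requiring intra-operative placement of suprapubic catheters as part of routine post-operative care", so the allocated device is handled in theatre.

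Under Description of Recruitment Methods, women being scheduled for surgery "will be approached about participating in the study in the pre-operative urogynecology clinic". Step 1 of the schedule is "Informed consent obtained pre-operatively to participate in study", so consent comes before randomisation. The target is "444 total, 222 per group", which implies 1:1 allocation.

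The Data Analysis section compares UTI with no UTI by Fisher's exact test. It also plans a multiple logistic regression on prior UTI, duration of catheterization, type of surgery, age, BMI and comorbid conditions.

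**The concern.** In a balanced block of 4, two women receive each catheter. Once one arm has used both its places, the rest of the block is known. Someone who sees the catheters in sequence and knows the block size can work this out without ever seeing the list, so locking the list away would not be enough.

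If that person also influences who is approached, or when a woman is operated on, a forecast could affect which women enter which arm. Two features make this more than a formality. The protocol states a hypothesis in favour of the silver-alloy catheter, and some prognostic information, such as history of past UTI, is known before randomisation. The resulting selection bias would pass straight into an unadjusted comparison of UTI rates.

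**Working it through.** **Inputs.** Block size 4 (schedule, step 3). Allocation 1:1, so 2 + 2 per block (inferred from 222 per group). Total 444, which is 444 / 4 = 111 blocks. The protocol states no predictability figure, so there is none to reproduce.

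**Certain allocations when every earlier one has been seen.** There are six equally likely orders: AABB, ABAB, ABBA, BAAB, BABA, BBAA.
- Positions 1 and 2 are never certain.
- Position 3 is certain when the first two match, which happens in 2 of 6 orders: 1/3.
- Position 4 is always certain: 1.

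Average = (0 + 0 + 1/3 + 1) / 4 = 1/3, and 444 × 1/3 = 148 women.

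**Best guess.** Choose the arm with more places left, and toss a coin if they are equal. The chance of being right by position is 1/2, 2/3, 2/3, 1. Average = (17/6) / 4 = 70.8%, against 50% under simple randomisation.

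**Effect of a lag.** Women are approached in clinic, and the catheter is seen later in theatre, so the most recent allocations may still be unseen when a decision is made.

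| Most recent allocations unseen | Certain, positions 1 to 4 | Average certain | Women of 444 | Best guess, positions 1 to 4 | Average right |
|---|---|---|---|---|---|
| 0 | 0, 0, 1/3, 1 | 33.3% | 148 | 1/2, 2/3, 2/3, 1 | 70.8% |
| 1 | 0, 0, 0, 1/3 | 8.3% | 37 | 1/2, 1/2, 2/3, 2/3 | 58.3% |
| 2 | 0, 0, 0, 0 | 0% | 0 | 1/2, 1/2, 1/2, 2/3 | 54.2% |

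With one unseen, position 4 is certain only if positions 1 and 2 matched (1/3), which gives (1/3) / 4 = 8.3%. With two unseen, only position 1 is known when position 4 is decided, so nothing is certain.

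**Alternatives, with every earlier allocation seen.** A fixed block of 6 still leaves 25% certain, and a fixed block of 8 leaves 20%. Randomly mixed sizes were simulated (300 runs of 444 women; the tracker knows the possible sizes but not their order). Blocks of 4 and 6 leave about 5.5% certain. Blocks of 4, 6 and 8 leave about 2.2%, or roughly 10 women.

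Best-guess accuracy hardly moves. It is 70.8%, 68.3% and 66.6% for blocks of 4, 6 and 8. Weighted by block length for an equal mix, (4 × 70.8 + 6 × 68.3 + 8 × 66.6) / 18 = 68.1%.

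**Possible scale of bias (assumption, not from the protocol).** Suppose selection shifted baseline UTI risk by d percentage points between arms among the certain allocations only. The overall bias is then d times the certain share. For d of 5 to 15 points this is 1.7 to 5 points at a share of 1/3, and 0.4 to 1.25 points at 1/12. The difference used in the Power Statement is 10%.

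**The case against.** A reader might infer that a third of this trial's allocations will be known in advance, or that the surgeons choose whom to enrol with that knowledge. The protocol supports neither. It does not say who obtains consent, who holds the list, when randomisation is done, or how many surgeons share the sequence. The one-third figure needs one observer who sees every allocation in order, knows where blocks start, and acts with no lag. Several surgeons, or an operating order that differs from the randomisation order, would lower it. That the block is fixed and that the operating team is unblinded are natural readings, but both are inferred from silence. Nor does silence on concealment show that none was used.

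Three further points stand.
- The logistic regression includes prior UTI, so some of the selection one would fear is adjusted for. It uses actual duration of catheterization, not the duration expected at enrolment, and it cannot reach unmeasured factors. The plan does not label Fisher's test as the primary analysis.
- Varying the block size mainly removes certainty. Guessing the arm that is behind needs no knowledge of block size and still succeeds about 68% of the time.
- A reader might also infer that the assessors' blind is broken. Learning one woman's catheter raises the chance of guessing another's in the same block only from 50% to 67%, and only if block membership is known. Two of the three UTI criteria are laboratory thresholds.

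These points limit the size of the concern. They do not remove it, because nothing in the protocol separates those who see allocations from those who recruit or schedule.

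**Conclusion.** The point holds as a cheap improvement to the design. It is neither an internal contradiction nor evidence that bias occurred. With a single stated block of 4, a 1:1 ratio and one unstratified list, between 0% and 33% of allocations (0 to 148 of 444) could be known with certainty. Where the trial falls in that range depends on how many recent allocations are still unseen when an enrolment or scheduling decision is made, and the protocol does not allow that to be determined. Any selection bias would go uncorrected in the Fisher comparison and be only partly corrected in the regression.

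**What to change.** In step 3 of the schedule, replace the block-of-4 wording with computer-generated permuted blocks of randomly varying size, for example 4, 6 and 8. Keep the sizes out of any document available to the clinical team. Add that someone not involved in enrolment holds the list and releases each allocation only after consent and confirmed eligibility. It would also help to state who enrols and when randomisation is done.

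This cuts certain allocations from at most 33% to about 2%. Best-guess accuracy falls only from 70.8% to about 68%, so the varying sizes should not be presented as making the sequence unpredictable. A larger fixed block is not an adequate substitute.

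The cost is a regenerated list, a short protocol change, a named list holder with a simple release procedure, and a possible final imbalance of a few women.

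### The power statement gives 400 as the size per group, but the recruitment target of 222 per group (444 in total) fits only if 400 is the evaluable total, 200 per group

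*Combined protocol and SAP*

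**What the plan says.** The sample size is justified in the Power Statement of the combined protocol and SAP. It takes its background rate from the centre's own experience with standard catheters used suprapubically ("a previously published data from our center reported a CAUTI rate of 19" per cent) and then says that "a conservative estimate of 10% reduction will be used in our sample size calculation".

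The size itself comes in two consecutive sentences. The first begins "To obtain 80% power, with a difference in UTI rate of 10" per cent, and continues "then the sample size per group that we hope to recruit is 400". The second says "we anticipate 10% drop-out so we will plan to recruit 222 per group, summing 444 total participants".

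Subject Population gives the same recruitment target, "444 total, 222 per group", and lists 444 women.

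The Power Statement gives no alpha, names no test, and does not say explicitly that 19% was the control rate in the calculation. Data Analysis gives a two-sided 0.05 level for the t-test on continuous variables ("Continuous variables will be compared using a two sided t-test with alpha ≤ 0.05 considered statistically significant") and assigns Fisher's exact test to the primary outcome ("Binary outcomes (UTI vs. no UTI) will be compared using Fisher"...).

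**The concern.** The first sentence asks for 400 in each group. The second makes an allowance for losses, which can only raise the number, yet ends at 222 in each group. Both cannot be right.

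The 400 is the only statement of how many evaluable women the trial needs. Read literally, the protocol needs 800 evaluable women and plans to recruit 444, so a reader could conclude that the trial is planned at about half its required size. If instead the words *per group* are misplaced, the target is consistent and only the justification is misstated. The document should not leave the reader to work out which applies.

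**Working it through.** **1. Drop-out arithmetic (no statistical assumption needed).** Inputs: 400, 10% drop-out, 222 per group and 444 in total, all from the Power Statement. Formula: number recruited = number evaluable / (1 − 0.10).

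| Reading of 400 | Recruit per group | Recruit in total |
|---|---|---|
| Evaluable total (200 per group) | 200/0.9 = 222.2 | 400/0.9 = 444.4 |
| Per group, as written | 400/0.9 = 444.4 | 800/0.9 = 888.9 |
| Stated in the protocol | 222 | 444 |

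The first row reproduces the protocol's targets, rounded to the nearest whole number. In reverse, 222 × 0.9 = 199.8 and 444 × 0.9 = 399.6. The second row is twice the stated targets.

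**2. What the power inputs require.** Inputs: 80% power and a 10-point difference (Power Statement); control rate 19% (Power Statement, assumed to be the rate used), hence 9% with the silver-alloy catheter; two-sided alpha 0.05 (assumed, because the document attaches it only to the t-test). Pooled normal formula, per group, with p̄ the mean of the two rates:

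n = [1.960·√(2p̄(1−p̄)) + 0.842·√(p1(1−p1) + p2(1−p2))]² / (p1−p2)²

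- 19% v 9%: p̄ = 0.14, so n = [1.960·√0.2408 + 0.842·√0.2358]² / 0.01 = 187.8, or 188 per group. With a continuity correction, 208.
- 20% v 10%: 199 per group, 398 in total. This is the closest match to 200 among the rates tried.
- Largest requirement for any two rates 10 points apart (55% v 45%): 391.3, or 392 per group. By this formula no 10-point difference needs 400 per group.
- With a continuity correction that maximum is about 411, but 400 is reached only for control rates of about 47% to 63%, far from 19%.
- Reading the 10% as a relative reduction (19% v 17.1%): about 6,431 per group, so this reading does not explain 400 either.

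**3. Power at the two candidate sizes, 19% v 9%.**

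| Per group | Normal approximation | Fisher's exact test (full enumeration) |
|---|---|---|
| 200 | 82.4% | 79.4% |
| 400 | 98.4% | 98.1% |

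The stated 80% lies between the two values at 200 per group; with Fisher's test, 80% is reached between 200 and 205 per group. At 400 per group the power is about 98%, and the fall detectable from 19% with 80% power would be about 7.1 points (to 11.9%), not 10.

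**The case against.** The strongest objection is about weight. The figures that govern the trial, 222 and 444, agree wherever they appear, and the sentence after the error shows what was probably meant. No procedure, analysis or recruitment target is affected. On that view this is a slip in one phrase. The limited effect is real and sets the size of the conclusion. It does not remove the error: the sentence is the only statement of the evaluable sample size, and it differs by a factor of two from what the target implies.

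A second objection is that the supporting calculation does not reproduce 200 exactly. By the pooled formula 19% v 9% gives 188 per group, which inflates to about 209 (188/0.9 = 208.9), not 222. A calculation at 20% v 10% (199 per group) comes closer, and there 200 per group would give about 80% power by the normal approximation and 77% with Fisher's test. This stands. The inputs rule out 400 per group but do not settle how 200 was obtained, so the sponsor should check the original calculation before changing the sentence.

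A third objection is that the wording leaves open whether the 10% is absolute or relative. A fall from 19% to 9% is a relative reduction of 10/19 = 53%, which lies within the quoted range of 27% to 73% if that range is relative, and so is not obviously conservative. That ambiguity is also real. It does not rescue 400 per group, but the correction should give both rates so that the intended reading is clear.

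**Conclusion.** The concern holds. The label on the 400 is wrong as written: 400 per group contradicts the next sentence and Subject Population, and nothing else in the document supports it. The per-group figure is twice the one that fits the recruitment target (400 against 200).

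The contradiction rests on the drop-out arithmetic alone. The supporting power figures also assume a 19% control rate, an absolute 10-point difference and two-sided alpha 0.05.

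The effect is confined to the justification of the sample size. On the absolute reading, 200 evaluable women per group gives close to the stated 80% power, so the error is not evidence that 444 is too few. The difference between 79% with Fisher's test and the stated 80% depends on the method, and the choice of 222 over 223 is rounding; neither is an error. The sentence should be corrected, but the design need not change on this account.

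**What to change.** Ask the sponsor to check the original calculation, including the 200 per group. If it is confirmed, replace the two sentences with wording such as:

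> 200 evaluable women per group (400 in total) are required; allowing for 10% drop-out, 222 per group (444 in total) will be recruited.

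Beside it, state the UTI rate assumed in each group, so that the 10% is clearly absolute or relative, together with alpha, its sidedness and the test. Name the method to which the stated power refers. If the inputs are 19% v 9% at two-sided 0.05, the power at 200 per group is about 82% by the normal approximation and about 79% with the planned Fisher's exact test.

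The cost is one or two sentences and a look at the original calculation. Recruitment does not change if 200 per group is confirmed. If it is not, the requirement and the target of 444 must be reconciled.
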